1.3 Sample Size

The sample size for the study is based on the primary effectiveness endpoint, weekly standardized Kt/V and the primary safety endpoint, the number of pre-specified, serious, device related, treatment emergent adverse events during a dialysis interval.

A hypothesis test that the treatment period mean weekly standardized Kt/V is statistically significantly greater than 2.1 will be carried out for both the In-Center and In-Home treatment periods. Given that the true treatment period mean Kt/V is 2.5 units, with one-sided $\alpha=0.025$, a sample size of $n=11$ subjects, each measured weekly for at least 8 weeks of treatment, will have >90% power to detect that the mean is statistically significantly greater than 2.1 in the treatment period. This sample size calculation assumed a standard deviation of 0.7 units,

based on Sands et al (2009)¹, and a within patient correlation of Kt/V values of $\rho=.50$. The sample size calculation was based on an asymptotic normal theory one sample test using variance estimates that included covariance terms for repeated (weekly) measurements on each patient with a block diagonal first order autoregressive (AR(1)) covariance structure.

For the safety endpoint, the needed sample size yields an estimate of the rate of pre-specified adverse events per 100 dialysis treatments in each treatment period (In-Center and In-Home use), to a margin of error of less than 1 event per 100 treatments. With a two-sided $\alpha=0.05$, in order to construct a 95% confidence interval on the rate of pre-specified adverse events per 100 dialysis treatments with half-width less than 1 event per 100 treatments, the sample size required would be $n=30$ subjects with 4 dialysis intervals per week for a minimum of 8 weeks (i.e., 30 subjects with a minimum of 32 treatments). The sample size calculation was based on an asymptotic normal theory one sample test using variance estimates that included covariance terms for repeated measurements (4 dialysis intervals per week for 8 weeks) on each patient with a block diagonal first order autoregressive (AR(1)) covariance structure. This sample size calculation assumed a standard deviation of 0.8 AEs per dialysis interval and a within patient correlation of pre-specified AE counts of $\rho=.50$.

Given the sample sizes necessary to satisfy the power requirements for the Kt/V endpoint and the composite safety endpoint, a sample size of $n=30$ subjects will be needed for the study.

2.0 Data Analysis Considerations

2.1 Types of Analyses

Data analyses will consist of analyzing safety and effectiveness data.

2.2 Analysis Populations

The following analysis populations will be used in the study:

Safety Population – The safety population will consist of all subjects who are enrolled in the study. All safety analyses will be conducted on the safety population.

Intent-to-Treat (ITT) Population – The ITT population will consist of all subjects who are enrolled in the study. The primary analysis set will be the ITT analysis set with no missing value imputation with a sensitivity analysis performed on the ITT with missing value imputation population.

Per-Protocol (PP) Population – The PP population will consist of all subjects who are enrolled in the study, have successfully completed at least 75% of their dialysis treatments, have at least one valid value of the primary effectiveness variable and have no major protocol deviations while enrolled in the study. A successfully completed dialysis treatment is defined as one completed as prescribed by the physician. A major protocol deviation is defined as any protocol deviation that affects the soundness of the data or a subject's rights. Subjects to be excluded from the PP analysis set, and the reasons for their exclusion, will be determined and documented prior to statistical analysis. These decisions will not be outcome-data driven.

The analysis of the primary efficacy endpoint will be conducted on ITT and PP populations.

2.2.1 Subgroup Definitions

There are no subgroup analyses planned for this study.

2.3 Missing Data Conventions

Subjects who did not finish the study but have accumulated partial data for the primary effectiveness endpoint, Kt/V, will have their missing data imputed. Missing data for Kt/V will be imputed by taking the average of the subject's non-missing Kt/V responses. The analysis of imputed data will be used as a sensitivity analysis relative to the primary effectiveness analysis that is conducted on non-imputed data.

For all other endpoints of the study, no missing value imputation will be used. That is, all analyses of endpoints other than the primary effectiveness endpoint will be based on the observed data (i.e., complete case analysis).

2.4 Interim Analyses

No interim analysis is planned for this study.

2.5 Study Center Considerations in the Data Analysis

A study center is defined as a treatment administration site or group of treatment administration sites under the control and supervision of the same Principal Investigator (PI). There will be no selective pooling of study centers.

2.6 Documentation and Other Considerations

The data analyses will be conducted using SAS© Software, version 9.4 or later.

3.0 Analysis of Baseline Characteristics and Disease History

3.1 Patient Characteristics and Demographics

Baseline and demographic characteristics will be summarized for all subjects in the safety population. Continuous variables (age, baseline height, baseline weight, and BMI) will be summarized via mean, standard deviation, median, range, and number of non-missing responses. Categorical variables (gender, race, and ethnicity) will be summarized via counts and percentages.

3.2 Medical History

The number and percentage of subjects reporting each medical history condition and each primary cause of end stage renal disease (ESRD) will be reported in a summary table for all subjects in the safety population.

4.0 Analysis of Effectiveness

4.1 Description of Effectiveness Variables

4.1.1 Description of Primary Effectiveness Variable

The primary effectiveness endpoint is the weekly standardized Kt/V for each subject during the In-Center and In-Home use periods of the study. The site will provide pre and post BUN values, which will be used to compute the single pool (Kt/V) and weekly standardized values (stdKt/V) for inclusion in the study database as follows^{2,3}:

$$Kt/V = -\ln(R - GFAC * T_hours) + (4 - 3.5 * R) * 0.55 * \text{Weight loss}/V$$

$$\text{stdKt}/V = \frac{168 * (1 - \exp\{-Kt/V\})}{t} * \frac{1}{\frac{1 - \exp\{-Kt/V\}}{Kt/V} + \frac{168}{N * t} - 1}$$

where

R = ratio of post-dialysis BUN to pre-dialysis BUN;
 GFAC = 0.0090 (modification factor based on dialysis frequency of 4/week);
 T_hours = dialysis session length, in hours;
 V = urea distribution volume, calculated based on gender;
 Weight loss = fluid removed as reported by Tablo;
 N = number of treatments per week; and
 t = treatment time in hours.

If subject is male, then $V = 2.447 - (0.09156 \times \text{age}) + (0.1074 \times \text{height}) + (0.3362 \times \text{weight})$. If subject is female, then $V = -2.097 + (0.1069 \times \text{height}) + (0.2466 \times \text{weight})$. In both formulas for V , weight is the post-treatment weight as reported by Tablo.

If multiple lab values are drawn for a subject during a given week, then the lab values for BUN in the computation of R will be those from the date/draw on which the site is basing clinical care.

As described in Section 2.3 of this SAP, subjects who have missing data for the single treatment Kt/V values will have their data imputed for a sensitivity analysis of the primary effectiveness endpoint. All Kt/V values that are missing will be replaced in the above formula for stdKt/V by the average of the non-missing Kt/V values for that subject.

For the subgroup analysis of subjects who dialyze 3 times per week, the GFAC modification factor will be set to 0.0080.

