6 STUDY DESIGN

6.1 Overview

This is a prospective, multicenter, open label, non-randomized, cross-over study. Subjects will be enrolled in the trial for approximately 21 weeks during which time Subjects will use the Tablo[™] Hemodialysis

System for dialysis treatments in all study phases. There are four periods during which the Tablo System will be utilized; run-in, treatment period 1, training/transition and treatment period 2.

• **Run-in** – Subjects will undergo dialysis treatment 4 times/week for 1 week In-Center. Treatments will be administered by study staff.

Confirmation of study eligibility will be assessed after the Subject completes this one-week run-in period.

• Treatment Period 1, In-Center – Subjects will undergo dialysis treatment 4 times/week for 32 treatments (approximately 8 weeks) In-Center. Treatments will be administered by study staff. Subjects are expected to undergo no more than 4 complete treatments per week during this treatment period.

Subjects are considered enrolled in the study if they meet all inclusion and exclusion criteria and have started the first study treatment during the first treatment period.

- In-Home Transition—Subjects will undergo device training for the study, then perform self-care dialysis 4 times/week for approximately 4 weeks. Treatments performed during the first portion will be completed In-Center under supervision. Treatments performed during the second portion will be completed In-Home. This second portion will assess subject stability in a new care environment. Supervision will be at the discretion of the Investigator.
- **Treatment Period 2, In-Home** Subjects will undergo self-care dialysis treatment 4 times/week for 32 treatments (approximately 8 weeks) In-Home. Subjects are expected to undergo no more than 4 complete treatments per week during this treatment period.
- **Follow-**Up---Subjects treatment modality will be followed for up to 5 years post study completion.

Figure 1: Study Design

Data collected during Treatment Period 1 and Treatment Period 2 will be used to assess the primary endpoints.

In the event a subject undergoes more than 4 complete treatments per week, during Treatment Period 1 and Treatment Period 2, the additional treatment(s) will be reported as a protocol deviation per Section 13.3.2.

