12.5 Missing Data

All missing values within the treatment period will be imputed using a multiple imputation procedure (Markov Chain Monte Carlo (MCMC) method). Parameter estimates and inferences for each treatment period will be based on the multiple imputations as described in Little and Rubin (2002). For subjects who did not finish the study but have accumulated partial data for the primary effectiveness endpoint, missing data for Kt/V will be imputed by taking the average of the subject's non-missing Kt/V responses.

For all other endpoints, missing value imputation will be described in the Statistical Analysis Plan (SAP).

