4.2 Analysis of Effectiveness Variables

4.2.1 Analysis of Primary Effectiveness Variable

The weekly standardized Kt/V values will be computed for each subject for the In-Center period and for the In-Home period. The following hypotheses will be tested at a one-sided $\alpha=0.025$ level of significance:

$$H_{a0}: \mu_{IC} \leq 2.1 \text{ vs. } H_{a1}: \mu_{IC} > 2.1$$

and

$$H_{b0}: \mu_{IH} \leq 2.1 \text{ vs. } H_{b1}: \mu_{IH} > 2.1$$

where μ_{IC} is the treatment period mean weekly standardized Kt/V value for the In-Center arm and μ_{IH} is the treatment period mean weekly standardized Kt/V value for the In-Home arm. These hypotheses will be tested using the Least

Square Mean for the respective treatment period from a repeated measures analysis of variance (RMANOVA) containing terms for subject, treatment arm (i.e., In-Center treatment period and In-Home treatment period), and time points (weeks) and using an AR(1) covariance structure.

Summary statistics (mean, sample size, standard deviation, minimum, maximum, and median) will be computed on the weekly standardized Kt/V values for each treatment period.

All analyses of the primary effectiveness variable will be performed on the ITT population with no missing value imputation, the ITT population with missing value imputation, and the PP population. The ITT population with no missing value imputation is the primary analysis set.

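### The SAP's only imputed analysis of stdKt/V fills gaps with a subject average that has no treatment-period limit and treats the fill as observed, so it tests home-phase dropout weakly

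*SAP*

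**What the plan says.** SAP 4.2.1 tests the In-Center and In-Home means separately against 2.1. It uses least-squares means from a repeated-measures model with subject, arm and week terms and AR(1) errors. "The ITT population with no missing value imputation is the primary analysis set", and an imputed ITT analysis serves as the sensitivity check. The SAP's table list gives that check three tables: 6, 10 and 11.

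The imputation rule appears in three places:

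- **SAP 2.3.** Who: "Subjects who did not finish the study but have accumulated partial data for the primary effectiveness endpoint, Kt/V, will have their missing data imputed". How: "Missing data for Kt/V will be imputed by taking the average of the subject's non-missing Kt/V responses".
- **SAP 4.1.1.** After referring back to 2.3, it covers all missing single-treatment values, which "will be replaced in the above formula for stdKt/V by the average of the non-missing Kt/V values for that subject".
- **Protocol 12.5.** First: "All missing values within the treatment period will be imputed using a multiple imputation procedure (Markov Chain Monte Carlo (MCMC) method", with inference for each period based on those imputations. Then, for subjects who did not finish, "missing data for Kt/V will be imputed by taking the average of the subject's non-missing Kt/V responses".

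Neither document limits the subject average to one treatment period. The SAP does not mention multiple imputation.

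**The concern.** The two periods are separate hypotheses, and the In-Home one is most exposed to dropout, because a subject can finish Treatment Period 1 and leave during transition or early at home. Such losses need not be random: Protocol 8.4 has the site confirm stability and skills during the transition. Protocol 7.6 keeps subjects lost to follow-up eligible for ITT.

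A sensitivity analysis should ask whether a positive In-Home result survives plausible assumptions about these subjects. This one assumes instead that they would have done at home what they did before going home, and it adds no uncertainty for that assumption. It can therefore look firmer than the observed-data analysis it is meant to stress. The documents also leave open which method is to be used and for whom, so two analysts could produce different versions of the three tables.

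**Working it through.** **The plan's own figure first.** SAP 1.3 assumes SD 0.7, rho 0.50 with AR(1), 8 weekly values, one-sided alpha 0.025, and "Given that the true treatment period mean Kt/V is 2.5 units". The variance factor for a mean of 8 AR(1) values is (1/64) x sum of 0.5^|i-j| = 0.3127. Then n = (1.960 + 1.282)^2 x 0.49 x 0.3127 / 0.4^2 = 10.06, rounded up to the stated 11 (power 92.3%). The inputs are therefore read as the SAP intends.

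**Assumptions the documents do not supply.** No dropout fraction or period difference is stated. I take n = 30 (SAP 1.3) and 6 subjects (f = 0.20) leaving before any home week. I also show f = 0.10 and f = 0.40; the latter is the ceiling implied by enrolling up to 50 for 30 evaluable, 20/50. Donor values are taken from Treatment Period 1, since "Data collected during Treatment Period 1 and Treatment Period 2 will be used to assess the primary endpoints". For simplicity the fill is made on the stdKt/V scale.

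**Shift in the estimate.** Write C and H for the In-Center and In-Home means, with s for stayers and l for leavers. Because the model contains subject terms, the observed-data In-Home least-squares mean already projects each leaver from their own In-Center level:

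- Observed: (1 - f) x Hs + f x (Cl + Hs - Cs)
- Imputed: (1 - f) x Hs + f x Cl
- Imputed minus observed: f x (Cs - Hs)

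Fitting the planned form (fixed subject, arm and week; AR(1) with rho 0.5 and SD 0.7 held known; a 4-week gap between periods; n = 30, 6 leaving) agrees:

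| Assumed In-Center / stayers' In-Home | Observed (SE) | Imputed (SE) | f x (Cs - Hs) |
|---|---|---|---|
| 2.5 / 2.2 | 2.20 (0.086) | 2.26 (0.071) | 0.2 x 0.3 = +0.06 |
| 2.5 / 2.5 | 2.50 (0.086) | 2.50 (0.071) | 0 |
| 2.3 / 2.5 | 2.50 (0.086) | 2.46 (0.071) | 0.2 x (-0.2) = -0.04 |

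The leavers' In-Center level cancels. With leavers at 2.2 and stayers at 2.5/2.2, the fit goes from 2.14 to 2.20 (+0.06). With leavers at 2.5 and stayers at 2.2/2.2, it stays at 2.26. For a stayers' difference of 0.3, the shift is 0.03, 0.06 or 0.12 at f = 0.10, 0.20 or 0.40.

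**Change in the standard error.** A hand check, ignoring the small correlation between periods: the variance of one subject's period mean is v = 0.49 x 0.3127 = 0.1532.

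- Observed: (v/n) x (1 + f)/(1 - f). At f = 0.20 this is 0.00511 x 1.5 = 0.00766, SE 0.088.
- Imputed, treated as complete: v/n = 0.00511, SE 0.071.

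The fitted values are 0.0862 and 0.0707. The observed SE by the hand formula is 0.079 at f = 0.10 and 0.109 at f = 0.40; the imputed SE stays at 0.071 throughout. If the 6 subjects leave after 4 home weeks, the effect is smaller: 0.0745 against 0.0707.

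**Both together.** In the first row, the distance from 2.1 in SE units goes from 0.10/0.0862 = 1.16 to 0.16/0.0707 = 2.26. These SEs omit between-subject variance because subject is a fixed effect, so only the comparison is meaningful.

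**The case against.** **Imputation affects only a sensitivity analysis.** This stands. A reader might infer that the rule could turn a failed trial into a success. It cannot: the success criterion uses the ITT set without imputation.

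**The pull toward In-Center is not a general bias.** This also stands. SAP 1.3 plans the same mean of 2.5 for each period, where the shift is zero, and if home delivery is higher the check is conservative. A reader might infer that the fill always favours In-Home; the documents give no period difference from which to say so.

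**The averaging window is unstated rather than declared to be the whole study.** True. A within-period reading is open for a subject with some home values, but cannot be carried out for one with none. Nor can it be said that the donors are purely In-Center: BUN is also drawn in run-in and transition, and part of the transition is at home. What is certain is that they precede Treatment Period 2.

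**Protocol 12.5 already provides multiple imputation.** It does, so this is the only imputed analysis in the SAP, not in the two documents together. But the SAP gives it no method and no table.

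**The smaller SE is legitimate if there is no period effect.** Correct, and that is the difficulty: the precision comes from assuming no period effect for the subjects on whom there is no home information.

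**The per-protocol analysis is another check.** It requires 75% of treatments. Counted against 64 scheduled treatments in the two periods, someone leaving before the home period reaches at most 32, or 50%, so that set drops these subjects rather than testing their absence.

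**Scale and scope.** The SAP fills single-pool Kt/V and then needs N and t for the missing week, which it does not supply, so the sizes above are illustrations. The mismatch over who is imputed is modest, since 4.1.1 refers to 2.3 and may be meant to inherit its scope; it matters for a completer with a missed draw.

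**Conclusion.** The concern holds for the SAP's imputed sensitivity analysis, Tables 6, 10 and 11, and for nothing beyond it. The fill has no period limit, carries no imputation uncertainty, and for subjects without home data can use only values from before Treatment Period 2. With 6 of 30 such subjects, SD 0.7 and rho 0.5, the In-Home SE falls by about 18% (0.0862 to 0.0707) whatever the period means are. The estimate shifts by f x (Cs - Hs), which is +0.06 under the assumed 2.5 and 2.2, zero under the planned equal means, and negative if home delivery is higher. The dropout fraction and any period gap are my assumptions. The loss of Protocol 12.5's multiple imputation from the SAP, and the difference between SAP 2.3 and 4.1.1 on who is imputed, are matters of text and need no assumption. This should be changed before analysis, but it does not put the primary result in doubt.

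**What to change.** 1. Delete the subject-average rule from SAP 2.3, SAP 4.1.1 and Protocol 12.5.
2. State one rule in both documents: multiple imputation combined by Rubin's rules, from a small model with subject and period effects and AR(1) errors, using Treatment Period 1 and 2 values. Say whether Kt/V or stdKt/V is imputed.
3. Name the imputed group once, in the same words in SAP 2.3 and 4.1.1 and in Protocol 12.5: either non-completers only, or everyone with a missing weekly value.
4. Add a delta (tipping-point) analysis for missing In-Home values, reporting how far they must fall before H_b0 is no longer rejected. This is the part that tests home-phase dropout directly, because imputation alone still leans on the subjects who stayed.

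The cost is a SAP revision and a wording amendment to the Protocol, with Sponsor and IRB approval if the change counts as significant under Protocol 14.4. Standard software suffices and no new data are needed. The sensitivity interval will be wider and may be less favourable.

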4.1.2 Description of Secondary Effectiveness Variables

The secondary effectiveness variables for this study are the following:

- the ultrafiltration (UF) rate (actual and prescribed)
- the UF volume (actual and prescribed)
- treatment time (actual and prescribed)
- UF rate success

4.2 Analysis of Effectiveness Variables

4.2.1 Analysis of Primary Effectiveness Variable

The weekly standardized Kt/V values will be computed for each subject for the In-Center period and for the In-Home period. The following hypotheses will be tested at a one-sided $\alpha=0.025$ level of significance:

$$H_{a0}: \mu_{IC} \leq 2.1 \text{ vs. } H_{a1}: \mu_{IC} > 2.1$$

and

$$H_{b0}: \mu_{IH} \leq 2.1 \text{ vs. } H_{b1}: \mu_{IH} > 2.1$$

where μ_{IC} is the treatment period mean weekly standardized Kt/V value for the In-Center arm and μ_{IH} is the treatment period mean weekly standardized Kt/V value for the In-Home arm. These hypotheses will be tested using the Least

Square Mean for the respective treatment period from a repeated measures analysis of variance (RMANOVA) containing terms for subject, treatment arm (i.e., In-Center treatment period and In-Home treatment period), and time points (weeks) and using an AR(1) covariance structure.

Summary statistics (mean, sample size, standard deviation, minimum, maximum, and median) will be computed on the weekly standardized Kt/V values for each treatment period.

All analyses of the primary effectiveness variable will be performed on the ITT population with no missing value imputation, the ITT population with missing value imputation, and the PP population. The ITT population with no missing value imputation is the primary analysis set.

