11.3 Analysis of Primary Endpoint

The study is based on the primary endpoints for effectiveness and interval estimates of the safety of the device. The study will be considered a success from a statistical standpoint if:

- 1. Both primary analysis variables pass their respective hypotheses, i.e., H_{a0} and H_{b0} below are rejected in favor of H_{a1} and H_{b1}, respectively,
- 2. The rate of pre-specified adverse events per dialysis interval is estimated to be within the specified error of estimation for each treatment period.

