11.4 Analysis of Weekly Standardized Kt/V

The following hypotheses will be tested at a one-sided α =0.025 level of significance:

$$H_{a0}$$
: $\mu_{IC} \le 2.1$ vs. H_{a1} : $\mu_{IC} > 2.1$

and

H_{b0}: $\mu_{IH} \leq 2.1$ vs. H_{b1}: $\mu_{IH} > 2.1$

where μ_{IC} is the treatment period mean weekly standardized Kt/V value for the In-Center arm and μ_{IH} is the treatment period mean weekly standardized Kt/V value for the In-Home arm. This hypothesis will be tested using the Least Square Mean for the respective treatment period from a repeated measures analysis of variance (RMANOVA) containing terms for Subject, arm and time points (weeks) and using an AR(1) covariance structure.

The weekly standardized Kt/V value will be calculated using the Leypoldt (Seminar in Dialysis, 17(2); March-April 2004) formula of:

Standard Kt/V (stdKt/V) = 168*(1-exp(-Kt/V))/t/((1-exp(-t/V))/(Kt/V)+168/(N*t) -1)

Where: N=number of treatments / week; t= treatment time in hours

Summary statistics (mean, sample size, standard deviation, minimum, maximum, and median) will be computed on the weekly standardized Kt/V values for each treatment period.

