5.2 Analysis of Safety Variables

The following describes the safety analyses to be performed for the study. Analysis of the primary safety variable will be performed on the ITT population. All other safety analyses will be performed on the safety population.

Pre-specified Adverse Events for Primary Safety Variable

For each treatment period, a 95% confidence interval will be computed on the pre-specified adverse event rate per dialysis interval. This confidence interval will be computed using the Least Square Mean for the respective treatment period from a generalized linear model containing terms for subject, treatment arm and time points (i.e., a repeated measures analysis using GEE) using a Poisson link function and AR(1) covariance structure. If the AE start date/time is missing, the AE will be counted in the interdialytic interval in which it was observed (if available) or will be randomly assigned (during the final data analysis for the study) to one of the interdialytic periods in the treatment period.

Summary statistics (mean, sample size, standard deviation, minimum, maximum, median) will be computed on the number of pre-specified adverse events per dialysis interval for each treatment period. The same summary

statistics will be calculated by treatment period for the rate of pre-specified adverse events per 100 dialysis treatments.

Additional Analyses of Pre-specified Adverse Events

A table will be provided to show the number and percentage of safety population subjects with at least one pre-specified AE by treatment period and overall for each dialysis treatment interval (treatment, interdialytic, pre-treatment).

A summary table will be constructed to display the following with respect to pre-specified AEs:

- Subjects with at least one pre-specified AE
- Maximum severity, per subject
- Highest relationship to device, per subject
- Highest relationship to treatment, per subject
- Subjects with at least one SAE
- Deaths

All Other Study-Emergent Adverse Events

A table will be provided to show the number and percentage of safety population subjects with at least one study-emergent AE by treatment period and overall for each dialysis treatment interval (treatment, interdialytic, pre-treatment). A similar table will also be provided to show the number and percentage of safety population subjects with at least one occurrence of an AE by categorization (pre-specified AEs or all other AEs) by treatment period and overall.

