	Renal Failure NOS	xxx (xxx%)
	Glomerulonephritis	xxx (xxx%)
	Polycystic Kidney Disease	xxx (xxx%)
	Other	xxx (xxx%)
Unspecified	xxx (xxx%)	

STATKING Clinical Services (month day, year)
 Source Program: xxxxxxxx.sas

Table 5. Summary of Weekly Standardized Kt/V by Treatment Period
 Outset Medical - Study No. 2014-01
 ITT Population (N=xxx)

Treatment Period	Mean	Std Dev	n	Min	Max	Median
In-Center	xxx	xxx	xxx	xxx	xxx	xxx
In-Home	xxx	xxx	xxx	xxx	xxx	xxx

STATKING Clinical Services (month day, year)
 Source Program: xxxxxxxx.sas

The format of this table will be repeated for the ITT population with missing value imputation and for the PP population.

Table 8. RMANOVA for Weekly Standardized Kt/V - Tests of Fixed Effects
 Outset Medical - Study No. 2014-01
 ITT Population (N=xxx)

Source	Tests of Fixed Effects			
	NDF	DDF	Type III F	Pr > F
Subject	xx	xx	xxx	xxx
Treatment Period	xx	xx	xxx	xxx
Week	xx	xx	xxx	xxx

STATKING Clinical Services (month day, year)
 Source Program: xxxxxxx.sas

The format of this table will be repeated for the ITT population with missing value imputation and for the PP population.

Table 9. RMANOVA for Weekly Standardized Kt/V - LS Means and Standard Errors
 Outset Medical - Study No. 2014-01
 ITT Population (N=xxx)

Treatment Effect	Level	Least Squares Mean (LSMean) and Standard Error (SE)		p-Value ^a
		LSMean	SE	
Treatment Period	In-Center	xxx	xxx	xxx
	In-Home	xxx	xxx	xxx

^a One-sided p-value for test of H0: Mean Weekly Standardized Kt/V ≤ 2.1 vs. H1: Mean Weekly Standardized Kt/V > 2.1.
 STATKING Clinical Services (month day, year)
 Source Program: xxxxxxxx.sas

The format of this table will be repeated for the ITT population with missing value imputation and for the PP population.

Table 14. Summary of Ultrafiltration Rate and Volume Actual vs. Prescribed by Treatment Period
 Outset Medical - Study No. 2014-01
 ITT Population (N=xxx)

Treatment Parameter	In-Center			In-Home		
	Mean	Std Dev	n	Mean	Std Dev	n
Prescribed UF Volume	xxx	xxx	xxx	xxx	xxx	xxx
Prescribed Treatment Time	xxx	xxx	xxx	xxx	xxx	xxx
Prescribed UF Rate	xxx	xxx	xxx	xxx	xxx	xxx
Actual UF Volume	xxx	xxx	xxx	xxx	xxx	xxx
Actual Treatment Time	xxx	xxx	xxx	xxx	xxx	xxx
Actual UF Rate	xxx	xxx	xxx	xxx	xxx	xxx
Success Rate ^a	xxx	xxx	xxx	xxx	xxx	xxx

^a Where success is ultrafiltration rate achieved within 10% of the prescribed rate.
 STATKING Clinical Services (month day, year)
 Source Program: xxxxxxxx.sas

The format of this table will be repeated for the PP population.

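### The Table 8 shell fits Subject as a fixed effect, so the standard error used to test each period's mean stdKt/V against 2.1 leaves out stable differences between subjects

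*SAP*

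**What the plan says.** Protocol 11.4 and SAP 4.2.1 test, separately for In-Center and In-Home, whether the period mean weekly stdKt/V exceeds 2.1, at one-sided 0.025. Each test uses the period's least-squares mean from a repeated measures analysis of variance. The protocol describes the model as "containing terms for Subject, arm and time points (weeks) and using an AR(1) covariance structure", and the SAP as "containing terms for subject, treatment arm (i.e., In-Center treatment period and In-Home treatment period), and time points (weeks) and using an AR(1) covariance structure". Neither says whether Subject is fixed or random, and neither mentions a random effect.

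The shells in SAP Appendix B are more specific. Table 8, titled "RMANOVA for Weekly Standardized Kt/V - Tests of Fixed Effects", has three rows (Subject, Treatment Period and Week), each with numerator and denominator degrees of freedom and a Type III F. Table 9 takes the one-sided p-value against 2.1 from the least-squares mean and its standard error.

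SAP 1.3 plans the Kt/V test as a one-sample test with SD 0.7 and correlation 0.50, using "variance estimates that included covariance terms for repeated (weekly) measurements on each patient with a block diagonal first order autoregressive (AR(1)) covariance structure". Protocol 11.3 requires that "Both primary analysis variables pass their respective hypotheses".

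**The concern.** Fixing Subject does no harm when the question is a within-subject contrast, such as In-Home against In-Center. The primary test is not a contrast. It compares a mean with a constant, and the sampling error of a population mean includes the variation between the subjects sampled. When each subject's level is a fixed parameter, that variation is absorbed into the parameters and leaves the standard error.

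The planned model agrees with the planning variance only if subjects have no persistent differences. That is what AR(1) with correlation 0.5 and nothing else implies: the week 1 to week 8 correlation would be 0.5^7 = 0.008. The documents make this a strong assumption. Protocol 8.2 allows session length of 160 to 240 minutes and blood flow of 300 to 400 ml/min. In SAP 4.1.1 the distribution volume V depends on sex, height and weight, and in men also on age.

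Both primary hypotheses are decided from this standard error. The imputed ITT analysis (Tables 10 and 11) and the per-protocol analysis (Tables 12 and 13) use the same model, so they cannot show the problem.

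**Working it through.** **Inputs.** From SAP 1.3: SD 0.7 (variance 0.49), correlation 0.50 with AR(1), 8 weekly values per period, true mean 2.5, n = 11 for Kt/V and n = 30 for the study. From SAP 4.2.1: null value 2.1, one-sided 0.025. **Assumed:** the share *s* of the 0.49 that is stable between subjects, which the documents do not give.

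**Step 1. Reproduce the plan's figure.** The variance of a subject's 8-week mean is 0.49 × f(φ), where f(φ) is the average of the 8 × 8 AR(1) correlation matrix: f = [8 + 2 Σ (8 − k) φ^k] / 64, k = 1 to 7. For φ = 0.5, f = 0.3127. With n = 11, SE = √(0.49 × 0.3127 / 11) = 0.118 and power = Φ(0.4/0.118 − 1.96) = 0.923. With n = 10, power is 0.898. The stated n = 11 for more than 90% power reproduces.

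**Step 2. Error of the fixed-Subject test at n = 30.**

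- Model variance = (1 − s) × 0.49 × f(φ) / 30
- True variance = model variance + s × 0.49 / 30
- Per-test error = P(Z > 1.96 × model SE / true SE)
- Both-test error, with both means at 2.1 and the same subject effect in both periods: bivariate normal with correlation (s × 0.49/30) / true variance

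There are two readings of the 0.50. In A it is the total lag-1 correlation, so φ = (0.5 − s)/(1 − s) and s cannot exceed 0.5. In B it is the residual correlation, so φ = 0.5 throughout.

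Example, reading A, s = 0.3: φ = 0.2/0.7 = 0.286 and f = 0.2075. Model variance = 0.7 × 0.49 × 0.2075/30 = 0.00237 (SE 0.049). True variance = 0.00237 + 0.0049 = 0.00727 (SE 0.085). The ratio is 0.571, and P(Z > 1.96 × 0.571) = 13.1%.

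| Share s | A: model SE / true SE | A: per test | A: both | B: per test | B: both |
|---|---|---|---|---|---|
| 0 | 0.071 / 0.071 | 2.5% | 0.1% | 2.5% | 0.1% |
| 0.1 | 0.064 / 0.076 | 4.9% | 0.7% | 4.6% | 0.6% |
| 0.2 | 0.057 / 0.080 | 8.4% | 2.6% | 7.2% | 1.8% |
| 0.3 | 0.049 / 0.085 | 13.1% | 6.3% | 10.2% | 3.8% |
| 0.4 | 0.041 / 0.090 | 19.0% | 12.1% | 13.4% | 6.6% |
| 0.5 | 0.032 / 0.096 | 25.7% | 19.6% | 16.9% | 10.0% |

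**Step 3. Check by simulation.** Subject, period and week were fitted as fixed effects with AR(1) by REML on complete data. Under A (2,000 runs each) the per-test error was 2.6, 5.4, 8.4, 13.7, 18.4 and 27.1% for s = 0 to 0.5. Under B (4,000 runs each) it was 4.4–5.2% at s = 0.1 and 16.7–18.4% at s = 0.5. Under B, n = 11 gave similar values, so the inflation depends on *s* and hardly on n. If half of the stable variance is subject-by-period, reading A gives 9.4% per test and 2.0% for both at s = 0.3, and 17.4% and 5.9% at s = 0.5.

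**Step 4. Check the remedy.** With random subject, random subject-by-period and AR(1) residual (REML, 29 df standing in for Kenward-Roger, balanced data, 1,000 runs each), the per-test error was 2.0% at s = 0, 2.7% at 0.3, 2.6% at 0.5, and 2.9% at 0.5 with half subject-by-period. Dropping Subject and keeping AR(1) alone is not enough: the error was about 3.0 to 5.4% for shares of 0.1 to 0.75 under B.

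**The case against.** **Subject may not really be fixed.** Neither model description uses the word, and SAP 5.2 uses similar wording for the safety model, which it glosses as "i.e., a repeated measures analysis using GEE". There, Subject could simply mean the repeated-measures unit. The fixed reading rests on one row of a mock table. This stands as a limit on certainty. But a programmer following Table 8 would fit the fixed-Subject model, and nothing else in either document says otherwise.

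**The target may be the enrolled subjects only.** For their mean, the fixed-Subject standard error is valid. The documents do not state the target. The population reading is the likelier one, because SAP 1.3 treats patients as independent sampled units carrying the full SD, but it is an inference.

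**The size is assumed.** No between-subject share is given, and the largest figures come from reading A. Reading B and the subject-by-period variant are lower. All of them point the same way.

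**The practical window is narrow.** Both tests must pass, so the both-test rate applies when both means are at 2.1, and it is 2.6% or less for shares up to 0.2. The per-test rate governs when one period is at 2.1 and the other clearly passes. At share 0.3 under A, the two analyses disagree only for an observed period mean between about 2.20 and 2.27. This limits the severity but does not remove the defect.

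**A richer random structure needs a fallback.** In a 150-run check, the subject-by-period variance was estimated at essentially zero in about 45–63% of runs when it was truly absent. This is usually harmless, but the SAP should say what is then done.

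**Conclusion.** The concern holds. As the Table 8 shell specifies it, the primary model gives a standard error that is too small for testing a population period mean against 2.1 whenever subjects differ persistently in stdKt/V. The error is modest at a between-subject share of 0.1 or less (under 5% per test). It is 10 to 13% per test at a share of 0.3, and 17 to 26% at 0.5, depending on how the 0.50 correlation is read.

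These sizes assume 30 subjects with 8 complete weeks per period and the SAP's SD of 0.7. The conclusion rests on two inferences: that Table 8 describes the model to be fitted, and that the target is a population mean. If the true mean is near 2.5, as planned, the expected decision is unchanged. The error matters if a period mean is close to 2.1. This should be corrected before analysis. It does not put the design in doubt.

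**What to change.** In Protocol 11.4 and SAP 4.2.1:

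- State that the target is the population mean in each period.
- Take Subject out of the fixed effects. Fit period and week as fixed, with a random subject effect, a random subject-by-period effect and an AR(1) residual within subject.
- Name a small-sample degrees-of-freedom method, such as Kenward-Roger.
- Give a rule for a variance estimated at zero or a fit that does not converge, for example dropping the subject-by-period effect and keeping the random subject effect.
- Test each period's least-squares mean against 2.1 from this model, and drop the Subject row from Table 8 and its repeats (Tables 10 and 12).

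A one-sample t-test on subject period means is a useful supportive check; on balanced simulated data it held its level (2.1–2.9% at n = 30 under B). It is equivalent to the mixed model only with balanced data. Those are not expected, because the primary analysis is unimputed and Protocol 7.6 allows withdrawn subjects to be replaced.

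The cost is wording, one model statement, one table row and larger standard errors. At n = 30 and a true mean of 2.5, power per test under A is about 99.5% at share 0.3 and 98% at share 0.5 (noncentral t, 29 df). Power for both tests is about 99% and 96%. Under B at share 0.5, power per test is about 97% (normal approximation). No larger sample is needed.
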